- 7) *Pharmacokinetic (PK) assay*: Determination of plasma concentration of ticagrelor and its active metabolite (AR-C124910XX) will be assessed from blood samples taken at the same time points of PD analysis as previously described [40]. Blood samples for measurement of drug concentrations will be drawn through the same cannula used for PD sampling. The blood will be taken into lithium heparin tubes and placed on ice until centrifugation (2800 rpm, 4°C, 10 min) within 30 min of sampling to collect the plasma, which will be transferred to plain polypropylene tubes and frozen upright at or below -20°C until analysis.

Primary and secondary objectives

The primary end point is the level of on-treatment platelet reactivity as assessed by VASP-PRI after treatment with ticagrelor 90mg bid on top of aspirin (81mg/day) for 7-10 days. The primary hypothesis of our study is that in DM patients the presence of CKD is associated with lower platelet inhibition (assessed by PRI determined by VASP-P) compared with those without CKD.

Additional objectives include:

- 1) The comparison of PD measures following administration of ticagrelor 90 mg between CKD and non-CKD groups at each time point assessed with PRU determined by the VerifyNow P2Y12 assay, 5 and 20 µM ADP-induced platelet aggregation by LTA and clot kinetic assessed by CORA[®] system.

- 2) The comparisons of level of platelet reactivity as assessed by multiple assays after treatment with ticagrelor 60 mg bid (on top of aspirin 81mg/day) for 7-10 days between the CKD and non-CKD groups.
- 3) The comparison of plasma concentrations of ticagrelor and its metabolite between the DM patients with and without CKD after 7-10 days of ticagrelor (60 and 90 mg) treatment.
- 4) The comparison of platelet inhibition by standard dose (90mg twice daily) versus low dose (60mg twice daily) of ticagrelor in DM patients with or without CKD.
- 5) The comparison of the rates of high on-treatment platelet reactivity (HPR), defined as VASP-PRI $\geq 50\%$, PRU > 208 , 5 μM ADP-induced maximal platelet aggregation $\geq 46\%$ or ADP induced MA > 47 (41,42).
- 6) To evaluate whether response to ticagrelor varies with the proportion of RPs in DM patients according to the CKD status.
- 7) To assess the effects of different levels of P2Y₁₂ inhibition with thromboxane levels.
- 8) The comparison of PD and PK measures according to the CKD classification based on markers of kidney damage (ACR).

Sample Size Computation and Power Analysis

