
The primary hypothesis of our study is that in DM patients the presence of CKD is associated with lower platelet inhibition compared with those without CKD after administration of ticagrelor 90 mg bid. Under the assumption of 10% absolute difference in mean PRI between CKD and non-CKD groups, with a common standard deviation of 13.0% a sample size of 37 patients per group will allow to detect a difference in platelet aggregation between the two

cohorts with a 90% power and two-sided $\alpha=0.05$ (22). Considering the two cohorts (CKD and non-CKD), 74 patients with a valid primary end point data will be needed. Assuming a 40% rate of invalid results due to hemolysis or drop-out, up to 102 patients will need to be randomized in the study. We anticipate to consent approximately 115 patients in order to reach the target number of patients. We have chosen a 10% absolute increase of PRI by VASP-P as reference value since this has been associated with a difference in clinical outcomes (43).

Statistical analysis plan

Categorical variables will be expressed as frequencies and percentages. Continuous variables will be presented as mean \pm SD or median [IQR] when appropriate. Continuous variables will be analyzed for normal distribution with the Kolmogorov-Smirnov test. Student's t-test will be used for comparison of normally distributed continuous variables. Wilcoxon test or Mann-Whitney's U test will be used for comparisons of continuous variables not following a normal distribution. An analysis of covariance (ANCOVA) method with a general linear model, using baseline variables significantly different between groups as covariates, will be used to evaluate the overall difference between groups and all between-groups comparisons, in line with other PK and PD studies (22,24). Analysis of variance (ANOVA) will be used to evaluate intragroup comparisons. In line with recommendations for cross-over study designs, treatment effects will be evaluated considering the functional parameters observed in the overall patient population after the treatment regardless of the sequence in which patients received treatment. Patients who will successfully complete at least one treatment phase of the study will be considered for comparisons. The absolute between-treatment mean differences and 95% confidence intervals will be estimated in the two groups. In order to perform an unbiased

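### Two analyses are prescribed for the primary CKD versus non-CKD comparison, and no rule says which one decides it

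*Combined protocol and SAP*

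**What the plan says.** The primary and secondary objectives section defines the endpoint: "The primary end point is the level of on-treatment platelet reactivity as assessed by VASP-PRI after treatment with ticagrelor 90mg bid". The sample size section repeats the hypothesis: "in DM patients the presence of CKD is associated with lower platelet inhibition compared with those without CKD after administration of ticagrelor 90 mg bid". The primary comparison is therefore of a continuous variable between two groups that patients belong to and are not randomised into.

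The statistical analysis plan then gives two rules that both cover it.

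- **Gated test.** "Continuous variables will be analyzed for normal distribution with the Kolmogorov-Smirnov test". If the variable passes, Student's method applies: "test will be used for comparison of normally distributed continuous variables". If it fails, a Wilcoxon or Mann-Whitney test is used.
- **ANCOVA.** A general linear model "will be used to evaluate the overall difference between groups and all between-groups comparisons". Its covariates are the baseline variables found to differ significantly between the groups. None is listed.

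The significance threshold of 0.05 is not attached to either rule. The sizing is for an unadjusted difference in means: "Under the assumption of 10% absolute difference in mean PRI between CKD and non-CKD groups". The spread is given in percentage points, "with a common standard deviation of 13.0", and the result is that "a sample size of 37 patients per group will allow to detect a difference in platelet aggregation between the two" groups.

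**The concern.** The gated test and the ANCOVA answer different questions. The first compares the groups as they are. The second compares them after adjustment for whatever happens to differ. If both are run and disagree, the plan gives no basis for saying which is the primary result, and the choice would be made with both p-values in view.

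Two features sharpen this. First, patients with and without CKD can be expected to differ in other ways too, so the adjusted and unadjusted estimates may differ by more than sampling noise. Second, the gated route can change the quantity tested: Mann-Whitney does not estimate the 10-point difference in mean PRI on which the trial is sized.

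**Working it through.** **1. The plan's own figure.** Inputs from the sample size section: difference 10, SD 13, two-sided 0.05, power 90%.

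- Normal approximation: n = 2 × (1.960 + 1.282)² × 13² / 10² = 2 × 10.51 × 1.69 = 35.5, so 36 per group.
- Two-sample t-test (noncentral t): 36.5, so 37 per group, with 90.4% power at 37.

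The stated 37 reproduces, and it is a t-test figure.

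**2. Type I error with no true imbalance.** Simulation of 10,000 null trials, 37 per group. Assumptions, none from the documents: Kolmogorov-Smirnov with Lilliefors correction at 0.05 in each group; 10 candidate baseline variables, two of them correlated 0.5 and 0.3 with PRI; covariates enter the ANCOVA only if they differ at p<0.05, as the plan prescribes.

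| Rule | Normal data | Skewed data (gamma, shape 2) |
|---|---|---|
| t-test alone | 4.9% | 5.0% |
| Mann-Whitney alone | 4.7% | 5.0% |
| ANCOVA alone | 4.2% | 4.3% |
| Gated t-test or Mann-Whitney | 5.0% | 5.3% |
| Gated test or ANCOVA, either significant | 5.7% | 6.7% |

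With a covariate correlation of 0.6 and 1 or 10 candidates, over normal and log-normal data, the last row runs from 5.0% to 6.3%. Hence roughly 5–7%. The gate contributes little; the excess comes from leaving the gated test and the ANCOVA unranked.

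**3. Disagreement under imbalance.** Assume no CKD effect beyond one covariate that differs by 0.4 SD between groups and correlates 0.5 with PRI.

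- Shift in the unadjusted mean difference: 0.4 × 0.5 × 13 = 2.6 PRI points.
- Chance that the covariate is significant and so enters the ANCOVA: 0.4 × √(37/2) = 1.72, and Φ(1.72 − 1.96) = Φ(−0.24), about 0.41. The adjustment is therefore applied in under half of such trials.
- Simulated share of trials in which the gated test and this ANCOVA fall on opposite sides of 0.05: about 9–12%.

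If the covariate is always adjusted for, imbalances of 0.3–0.5 SD and correlations of 0.3–0.5 give disagreement between t-test and ANCOVA in 5–18% of trials.

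**4. Sensitivity of the gate.** The plan does not state the form, level, or pooled or by-group use of the Kolmogorov-Smirnov test. Rejection rates at n = 37:

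| Distribution | Uncorrected | Lilliefors-corrected |
|---|---|---|
| Log-normal (sigma 0.4) | 2% | 40% |
| Gamma (shape 2) | 4% | 56% |
| Beta(2,8) | under 1% | 30% |

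The unstated form largely decides which test would be used on skewed data.

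**5. Sample size with one fixed model.** With covariates unrelated to group, power at 37 per group (normal approximation) is 91.1%, 93.4% and 96.9% for assumed covariate–PRI correlations of 0, 0.3 and 0.5. Imbalance costs some of this gain. At 0.4 SD, the squared correlation between group and covariate is 0.16 / (0.16 + 4) = 0.038, so the variance rises by 1 / (1 − 0.038) = 1.04. With a correlation of 0.5, n = 35.5 × 0.75 × 1.04 = 27.7, so 28 per group, still below 37. For comparison, Mann-Whitney as the single test on normal data would need 36.5 / 0.955 = 38.2, so 39 per group.

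**The case against.** The best defence is that the plan can be read as consistent. The t-test and Mann-Whitney sentences follow the descriptive-statistics sentences and may be meant for general tables, while the later and more specific sentence gives all between-group comparisons to the ANCOVA. This is plausible, but the text does not state that precedence, and the sample size rests on an unadjusted comparison of means. Even on this reading, the covariates are still picked from the data.

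It is also fair to say that the type I error figures suppose someone claims whichever result is significant. The documents do not say that this will happen. The figures measure what the wording permits, not what is planned.

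Three stronger readings might be inferred, and the documents do not support them.

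- **Three tests are open to free choice.** The t-test or Mann-Whitney choice follows a stated rule. It depends on the data, but for one dataset only two routes remain.
- **The type I error exceeds 8%.** Figures of that size arise if the ANCOVA always adjusts for a strong covariate. Under the plan's significance rule and no true imbalance, the ANCOVA usually has few or no covariates and stays close to the t-test.
- **The normality test cannot detect skewness at this sample size.** That holds only for the uncorrected form, which the plan does not specify.

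**Conclusion.** The point holds as a conflict between two stated rules for the primary endpoint, with no order between them. The effect on type I error is modest: roughly 5–7% if either result counts, with no true imbalance and the assumptions in step 2. The more important consequence is that the two routes can give different conclusions, in about 9–12% of null trials under the assumed 0.4 SD imbalance and 0.5 correlation. The documents give neither of these two values, so the percentage is illustrative. The possible change from a mean difference to a Mann-Whitney comparison is a separate, secondary reason to settle the matter.

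The normality gate on its own is not a material source of error. Nor does the defect undermine the sizing: 37 per group reproduces and remains adequate for a single pre-specified model.

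**What to change.** For the primary endpoint, replace both the normality gate and the significance-selected covariates with one linear model of VASP-PRI on 90 mg. Its terms should be CKD group, treatment period (90 mg falls in phase 1 or phase 2 depending on sequence) and a short covariate list fixed before the data are seen. The list should leave out GFR, which defines the groups. Report the mean difference with its 95% CI and state that this model alone tests the primary hypothesis at 0.05. Label the unadjusted t-test and the Mann-Whitney test as sensitivity analyses. Robust standard errors are optional.

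The cost is wording in the statistical analysis plan. No patients, visits or assays are added.

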Diabetes mellitus (DM) and chronic kidney disease (CKD) represent pandemic diseases and a major public health concerns because of their prevalence and poor cardiovascular prognosis (1-3). DM is the most common cause of CKD and up to 40% of diabetic patients develop CKD (4). CKD was present in approximately one-third of patients with NSTEMI-ACS and was a powerful independent predictor of subsequent mortality (5). Importantly, patients with DM or CKD have a high thrombotic milieu and frequently experience recurrent atherothrombotic events (6-11). Multiple mechanisms may contribute to these observations, including accelerated platelet turnover rates (12,13). These observations underscore the importance of antiplatelet therapy for prevention of atherothrombotic recurrences in these high-risk patients. Clopidogrel is the most widely used platelet P2Y₁₂ receptor inhibitor. However, despite its clinical benefit, patients with DM and CKD frequently experience recurrent atherothrombotic events. The high atherothrombotic recurrence rates in DM and CKD patients are partly due to the inadequate response to antiplatelet agents, in particular clopidogrel, which is enhanced with the co-existence of these disorders (14-17). Therefore, identifying antiplatelet agents with more favorable pharmacokinetic (PK) and pharmacodynamics (PD) profiles is of key importance.

Ticagrelor represents an attractive strategy especially in high-risk patients, such as those with DM and/or CKD (18-20). Ticagrelor, a cyclopentyltriazolopyrimidines, is an oral, reversible, non-competitive P2Y₁₂ receptor inhibitor with rapid onset and offset of action and provides a stronger and more consistent platelet inhibition than clopidogrel (21-23). Although ticagrelor is a direct acting agent, ~30% of its effects are attributed to a metabolite (AR-C124910XX) derived from hepatic metabolism (23). In the large scale phase III PLATO (Platelet Inhibition and Patient Outcomes) trial conducted in ACS patients, ticagrelor, in addition to

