estimation of the treatment effect, period and sequence effects, which may occur in crossover studies, will be evaluated. A p-value <0.05 will be considered statistically significant. Statistical analysis will be performed using a SPSS v22.0 software.

Publication Strategy/Additional Information

This study will be performed at the University of Florida Health Science Center at UF Health - Division of Cardiology. Patients will be recruited and consented at the Cardiology clinics in the UF Health system. Patients will be screened by cardiology research, who will verify that all candidates meet inclusion criteria. Subjects will be identified with a number and data collection sheets will all be stored in a locked area. Data will be kept for 6 years after enrollment ends to comply with HIPAA regulations. Patients will receive a handout with the names and telephone numbers of the doctors involved in the study. Patients will sign an informed consent relating to the study. Study subjects will be identified first (months 1-18): we expect to enroll 4-5 subjects monthly and complete enrollment in 18 months (total: 82 subjects enrolled). Months 19-20 will be implied for statistical analysis and months 21-22 for manuscript preparation.

We anticipate no major problems with the described protocol since the approach is a straight forward prospective study and is based on well-established methods. However, since there is limited experience with to define platelet function in this specific subset, variability may be higher than expected and we cannot currently perform a detailed sample size calculation. We anticipate adding this to the protocol after inclusion of the study population has been completed. If the sample size after one year is estimated to be too small, additional patients will be included. This approach is in agreement with recommendations for pilot investigations (44).

Possible Discomforts and Risk

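### CKD versus non-CKD is compared with equal-variance methods although neither equal group sizes nor equal spread is secured; Welch's test and a robust-variance ANCOVA are a cheap safeguard

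*Combined protocol and SAP*

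**What the plan says.** The primary hypothesis concerns VASP-PRI on ticagrelor 90 mg, CKD versus non-CKD. Two statements in the Statistical analysis plan section bear on how it is tested:

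- "Student's t-test will be used for comparison of normally distributed continuous variables". The only distributional check named is for normality. There is no check of variances and no unequal-variance version.
- An ANCOVA with a general linear model "will be used to evaluate the overall difference between groups and all between-groups comparisons". The section does not say whether the t-test or the ANCOVA is primary for the CKD contrast.

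The Sample Size Computation and Power Analysis section takes as its target a "10% absolute difference in mean PRI between CKD and non-CKD groups". One SD is used for both groups, and the size follows from it: "with a common standard deviation of 13.0% a sample size of 37 patients per group". The power is 90% at a two-sided alpha of 0.05. The section also allows for 40% invalid results or drop-out.

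Under Research design, CKD status is assigned from estimated GFR. The 1:1 randomisation is to dose sequence, so it does not set the ratio of CKD to non-CKD patients. No quota or cap per group is stated. The eighth additional objective repeats the PD and PK comparisons with CKD redefined by albuminuria (ACR). That split is exploratory and has no size target.

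**The concern.** A pooled-variance test keeps its level if the two SDs are equal or the two groups are of nearly equal size. The plan aims for the second condition and assumes the first, but secures neither. CKD status is a patient characteristic, so even if the mean PRI is the same in both groups, nothing makes the spread the same. Enrolment by clinic attendance need not give 37 and 37, and the anticipated losses need not fall equally.

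If the smaller group has the larger SD, the pooled standard error is too small and false positives exceed 5%. If it has the smaller SD, the standard error is too large and power is lost. The ordinary ANCOVA behaves in the same way because it also uses one residual variance. At stake are the p-value of the primary contrast, the secondary CKD comparisons of continuous measures, and any confidence interval reported for CKD minus non-CKD. The ACR-based split is the most exposed, since not even a 37/37 target applies to it.

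**Working it through.** **Inputs.** From the sample-size section: difference 10, common SD 13, 37 per group, 74 valid patients, two-sided 0.05, 90% power. Assumed, because the documents give none: splits of 30/44, 24/50 and 20/54 (CKD first), and SD pairs from 15 vs 12 to 18 vs 10, plus the reverse case 11 vs 16.

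**1. The plan's own figure.** Normal approximation: n = 2(1.960 + 1.282)² × 13² / 10² = 35.5, so 36 per group. The exact calculation for the pooled t-test gives power 89.6% at 36 and 90.4% at 37. The stated 37 is reproduced, and it is the equal-variance t-test figure.

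**2. Why the level moves.**

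- True SE of the difference: √(s₁²/n₁ + s₂²/n₂).
- SE used by Student's test (approximately): √{[(n₁−1)s₁² + (n₂−1)s₂²]/(n₁+n₂−2) × (1/n₁ + 1/n₂)}.
- With r = used SE / true SE, the actual level is about 2Φ(−1.96 r).

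At 24/50 with SD 16 in CKD and 11 in non-CKD:
- True SE = √(256/24 + 121/50) = √13.087 = 3.618.
- Pooled variance = (23 × 256 + 49 × 121)/72 = 164.1. Used SE = √(164.1 × 0.06167) = 3.181.
- r = 0.879; level ≈ 2Φ(−1.723) = 8.5%.

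At 24/50 with SD 11 in CKD and 16 in non-CKD:
- True SE = √(121/24 + 256/50) = 3.188.
- Pooled variance = (23 × 121 + 49 × 256)/72 = 212.9. Used SE = 3.623.
- r = 1.137; level ≈ 2.6%.

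When n₁ = n₂ the two formulas coincide, so r = 1 whatever the SDs. When s₁ = s₂, r = 1 whatever the split.

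**3. Simulated type I error of Student's test** (normal data, nominal 5%):

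| SD CKD / non-CKD | 37/37 | 30/44 | 24/50 |
|---|---|---|---|
| 13 / 13 | 5.0% | 5.0% | 5.0% |
| 15 / 12 | 5.0% | 6.0% | 7.0% |
| 16 / 11 | 5.0% | 6.7% | 8.4% |
| 18 / 10 | 5.1% | 7.8% | 10.5% |
| 11 / 16 | 5.1% | 3.7% | 2.7% |

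Simulation runs of different length agreed within 0.2 points (for example 7.6% to 7.8% for 18/10 at 30/44). Welch's test stayed at about 5.0% in every cell.

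**4. ANCOVA.** With one covariate and SDs 16 vs 11, the ordinary ANCOVA gave about 6.5% to 6.8% at 30/44 and 8.1% to 8.5% at 24/50. With 11 vs 16 it gave 2.8% at 24/50. A heteroscedasticity-robust (HC3) variance gave about 4.5% to 5.0%.

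**5. Power for a 10-point difference if both SDs are 13:**

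| Split | Student | Welch | Cost |
|---|---|---|---|
| 37/37 | 90.4% | 90.4% | 0 |
| 24/50 | 86.4% | 85.8% | 0.6 points |
| 20/54 | 82.6% | 81.4% | 1.2 points |

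Where the larger group has the larger SD, Welch gains power. At 25/49 with SD 13 in CKD and 19.5 in non-CKD, power is 64.1% for Student and 73.4% for Welch.

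**The case against.** The strongest reply is that the plan sizes the study at 37 per group, and at that split the pooled test holds 5.0% to 5.1% even with a twofold SD ratio. Unequal sizes alone do no harm either; both conditions must fail together. Pooled tests are conventional when equal groups are planned, and the plan contains no contradiction or arithmetic error on this point. All of this stands, and it is why the point is minor. What remains is that 37/37 is a target without a mechanism behind it.

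Four stronger readings are tempting, and the documents do not support them:

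- *The protocol concedes unequal spread.* The Publication Strategy/Additional Information section says "variability may be higher than expected", but this concerns overall variability and the sample size. A larger SD common to both groups leaves Student's test at 5%.
- *The Background forecasts an uneven split.* It says "CKD was present in approximately one-third of patients with NSTEMI-ACS" and that up to 40% of diabetic patients develop CKD. Neither describes clinic patients with diabetes and documented CAD on aspirin and clopidogrel, so neither forecasts enrolment.
- *The planned confidence intervals are wrong.* The only 95% interval the plan names is for the difference between doses within each CKD group. That contrast is largely within-patient, and a two-sample Welch interval does not apply to it.
- *Replacing the t-test is enough.* The plan gives the ANCOVA to all between-group comparisons, so changing the t-test alone would leave the CKD contrast unprotected.

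**Conclusion.** The point holds as a conditional, low-severity improvement. The plan uses equal-variance methods for a contrast between observed groups without securing equal sizes or equal spread. If both differ, the 5% level becomes about 6.0% to 7.8% at 30/44 and 7.0% to 10.5% at 24/50 when CKD has the larger SD, and about 3.7% and 2.7% when it has the smaller SD. Coverage of a pooled 95% interval for CKD minus non-CKD would be 100% minus these figures.

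These sizes rest on assumed splits and SD pairs, normal data and 74 valid patients. A reader might infer that the primary test as planned has an inflated error rate. That does not follow: at 37/37, or with equal SDs, the distortion is nil or negligible, and no passage shows that the SDs differ.

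**What to change.** In the Statistical analysis plan section:

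1. For CKD versus non-CKD comparisons of normally distributed continuous measures, including the ACR-based split, specify Welch's unequal-variance t-test in place of Student's.
2. In the ANCOVA of the same contrast, use heteroscedasticity-robust standard errors or separate residual variances by CKD group.
3. Apply the same variance treatment to any confidence interval reported for CKD minus non-CKD. Leave the within-patient dose contrast as it is.

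The cost is two or three sentences of wording, plus a check that the named software version can fit the robust or group-specific variance. The sample size stays at 37 per group. The change is nearly free rather than free: if the SDs are in fact equal, the power loss is nil at 37/37, about 0.6 points at 24/50 and 1.2 points at 20/54.

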The proposed investigation is a prospective, randomized, cross-over, open-label, PD and PK study in which CAD patients with DM on low-dose (81mg) aspirin and standard-dose (75mg) clopidogrel will be prospectively recruited. Patients will be screened during their regularly scheduled outpatient visits and informed about the study. Patients will be stratified according to CKD status into CKD and non-CKD groups. CKD will be defined according to the functional definition of the KDIGO (Kidney Disease: Improving Global Outcomes) guidelines (CKD: glomerular filtrate rate [GFR] $<60\text{ml}/\text{min}/1.73\text{m}^2$; non-CKD: $\text{GFR} \geq 60\text{ml}/\text{min}/1.73\text{m}^2$) (32,33). The rationale for considering the functional classification to initially stratify patients is in line with clinical studies showing the increased cardiovascular risk and markedly dysfunctional platelets according to GFR strata (10,11,16). For patient stratification, GFR will be estimated through the CKD-EPI (chronic kidney disease epidemiology collaboration) equation, as this is suggested by guidelines as the most accurate method to calculate GFR, especially for values in the normal range (above $60\text{ml}/\text{min}/1.73\text{m}^2$) (32,33). For comparison, GFR will also be calculated with the MDRD (modification of diet in renal disease) equation. In addition, as exploratory analysis, renal function will also be classified according to markers of kidney damage, in

particular albuminuria, in order to obtain a more comprehensive information about CKD (32,33). Albuminuria will be evaluated as albumin-to-creatinine ration (ACR) expressed in mg/g, which is approximately equivalent to albumin excretion rate. According to KDIGO guidelines, CKD will be defined as ACR >30mg/g and non-CKD as ACR ≤30mg/g (32,33). Albuminuria will be measured on random untimed spot urine samples. DM will be defined according to World Health Organization criteria and all subjects with DM will need to be on treatment with oral hypoglycemic agents and/or insulin for at least 2 months without any changes in their regimen (34).

After providing informed consent, eligible patients will be divided into CKD group and non-CKD group as described above. DM patients with CKD or without CKD will be randomized in a 1:1 fashion to one of the following treatment arms:

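### ANCOVA covariates for the non-randomised CKD comparison are chosen by baseline significance, with no named list and no exclusions

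*Combined protocol and SAP*

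**What the plan says.** The primary end point is VASP-PRI after 7–10 days of ticagrelor 90 mg twice daily. The primary hypothesis is that CKD is associated with lower platelet inhibition (Primary and secondary objectives).

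The groups are formed by kidney function. Under Research design, "CKD will be defined according to the functional definition of the KDIGO" guideline, with a GFR cut at 60 by the CKD-EPI equation, and "eligible patients will be divided into CKD group and non-CKD group as described above". Randomisation comes after that: "DM patients with CKD or without CKD will be randomized in a 1:1 fashion" to one of two dose sequences. A second GFR is also available: "For comparison, GFR will also be calculated with the MDRD (modification of diet in renal disease) equation". Objective 8 regroups patients by urinary albumin-to-creatinine ratio (ACR).

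The Statistical analysis plan gives an ANCOVA "using baseline variables significantly different between groups as covariates, will be used to evaluate the overall difference between groups and all between-groups comparisons". No section names candidate covariates, forces any into the model or keeps any out. The only significance threshold stated is p<0.05. The same section says that a "t-test will be used for comparison of normally distributed continuous variables", with rank tests otherwise. The sample size is set "with a common standard deviation of 13.0% a sample size of 37 patients per group". Baseline PD assessments are taken while patients are on clopidogrel.

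**The concern.** Patients with and without CKD can be expected to differ in ways that also affect platelet reactivity. Covariate adjustment is the only protection the plan offers against this in its primary contrast; the period and sequence checks concern the dose crossover. Three features of the selection rule weaken that protection.

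- **It tests the wrong thing.** A baseline p-value depends on sample size and does not measure whether a variable confounds the comparison. In small groups a real confounder can easily miss p<0.05.
- **It excludes nothing.** GFR differs between the groups by construction, so it satisfies the written rule. The same holds for MDRD GFR and, in the ACR-based comparison, for ACR. Adjusting for a variable that defines the groups removes much of the contrast under study.
- **It leaves a question of substance to chance.** The Background says that response to clopidogrel is impaired in DM and CKD. Adjusting for on-clopidogrel PRI asks whether CKD matters among patients with the same clopidogrel response, which is a different question from the unadjusted one. That choice should not depend on whether a baseline test reaches p<0.05.

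At stake are the estimate and p-value for the primary hypothesis, because the model that produces them is settled only after the baseline data are seen.

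**Working it through.** **Inputs from the documents:** difference 10 PRI points, SD 13.0, 37 per group, two-sided alpha 0.05, power 90%. **Assumed, because the documents give no figures:** number of confounders, their imbalance, their correlation with PRI and with each other, and the separation of GFR between groups.

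**1. The plan's own figure.** Normal approximation: n = 2(1.960 + 1.282)² × 13² / 10² = 35.5, so 36 per group. The exact two-sample t-test gives power 0.896 at 36 and 0.904 at 37. The stated 37 reproduces, as an unadjusted t-test.

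**2. Chance that the rule selects a truly imbalanced variable.** This is the power of a two-sample t-test with noncentrality d × √(37/2) and 72 degrees of freedom.

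| True imbalance d (SD) | 0.2 | 0.3 | 0.4 | 0.5 | 0.6 |
|---|---|---|---|---|---|
| Selected at p<0.05 | 14% | 25% | 40% | 56% | 72% |

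**3. Bias and type I error, simulated with no CKD effect.** With K independent confounders, each with imbalance d and correlation r with PRI, the unadjusted bias is K × r × d × 13. For K = 3, r = 0.3, d = 0.4 this is 3 × 0.3 × 0.4 × 13 = 4.7 points. Simulated type I error over d = 0.3–0.5 and r = 0.2–0.3:

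| Independent confounders | Significance rule |
|---|---|
| 1 | 4.9–5.7% |
| 2 | 5.4–6.6% |
| 3 | 6.1–8.7% |
| 4 | 7.1–11.8% |

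Across this grid the rule leaves a bias of 0.3–2.5 points. A complete fixed list gives 4.6–5.3% and a bias near 0. No adjustment gives 5.7–71.7% and 0.8–7.8 points.

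The results depend on independence. With three confounders correlated 0.4 with each other (r = 0.3 with PRI, d = 0.3–0.5), the rule gives about 5–6% and leaves 0.3–0.6 points of bias.

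**4. An incomplete fixed list, three independent confounders, no CKD effect.** Type I error:

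| (d, r) | (0.3, 0.2) | (0.4, 0.2) | (0.4, 0.3) | (0.5, 0.3) |
|---|---|---|---|---|
| Significance rule | 6.4% | 6.6% | 8.4% | 7.9% |
| List holding two of three | 5.9% | 6.4% | 8.2% | 10.0% |
| List holding one of three | 8.1% | 10.4% | 17.4% | 25.0% |

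**5. If GFR were entered.** A covariate separated by d SD inflates the variance of the CKD estimate by 1 + d²/4. For d = 2 the factor is 2.0: the standard error rises from 13√(2/37) = 3.02 to 4.27 and power falls to 65%. For d = 3 the factor is 3.25, the standard error 5.45 and power 45%. Simulation with GFR truncated at the group boundary (mean gap 22–56) gives 29–49%. Taken together, about 30–65%.

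**6. Power of a complete three-variable list for a 10-point effect:** 85% if the covariates are unrelated to PRI, up to 94% at r = 0.3.

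**The case against.** The strongest reply is that the demonstrated harm is modest and depends on assumptions. This stands. With one confounder, or with correlated ones, type I error stays near 5–6%. The 12% figure needs four independent confounders at the strong end of the range, and baseline variables in CKD patients need not be independent.

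A second reply is that a fixed list is better only if it is nearly complete. This also stands: with two of three confounders listed, results are similar to the rule's and in one setting worse; with one of three they are clearly worse. It limits the remedy without making selection by p-value sound.

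A third is that the hypothesis speaks of association, so the crude difference is itself of interest. That is a reason to report it, and the plan nevertheless chooses an adjusted analysis.

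Four stronger readings are tempting and are not supported:
- *That the plan leaves the deciding test open.* The text assigns the ANCOVA to all between-group comparisons, and the t-test sentence reads as generic. Sizing a trial by a t-test does not make that test a rival primary analysis. A sentence of confirmation is enough.
- *That the rule misses most moderate imbalances.* It misses most at 0.4 SD and below; at 0.5 SD it selects more than half.
- *That GFR will be in the model.* The wording admits it, but a sensible analyst may leave it out.
- *That covariates should instead be added when imbalance exceeds a size such as 0.2 SD.* That rule is also data-driven. At 37 per group a variable with no true imbalance exceeds 0.2 SD 39% of the time, and the rule could bring back on-clopidogrel PRI or reticulated platelets.

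**Conclusion.** The concern holds as a defect of specification in the primary analysis, and it should be fixed. What the text says, and what it does not exclude, is certain. The selection probabilities of 14–56% for imbalances of 0.2–0.5 SD follow from 37 per group alone.

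The size of the harm is not certain, because the documents contain no covariate data. It ranges from negligible (type I error about 5–6% with a single confounder or correlated ones) to moderate (about 6–12% with three or four independent ones). The loss of power to about 30–65% applies only if GFR is actually entered, and its size follows the assumed GFR separation. A reader might infer that the primary result will be materially wrong; the documents do not support that. They support the narrower conclusion that the protection against confounding is weaker than it need be and that two choices of substance, on kidney measures and on baseline PRI, are not made in advance.

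**What to change.** Amend the Statistical analysis plan before the outcome data are examined:

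1. Replace the significance rule with confounders named in advance on clinical grounds. The investigators should choose them from baseline data already collected, making the list as complete as 74 patients allow.
2. State that GFR (by either equation), creatinine and ACR are not covariates where they define or proxy the groups.
3. State whether on-clopidogrel PRI is in the primary model, and why.
4. Leave out variables studied as mechanisms. Reticulated platelets are the clear case: the Background cites platelet turnover, and objective 6 examines it by CKD status.
5. Confirm that this ANCOVA decides the primary VASP-PRI comparison on 90 mg, and report the unadjusted difference beside it.
6. If a sensitivity analysis is wanted, use a second, wider list that is also named in advance.

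The cost is wording only, with no added patients or samples. There are two downsides. A fixed list protects only against what it contains, and one that omits most confounders can do worse than the current rule (8–25% against 6–8% type I error when it holds one of three). Power may also differ somewhat from the stated 90%, at about 85–94% in the settings tried.
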